
Carretero et al⁹⁶ recently attempted to replicate the Sampson findings using similar parameters but in a larger sample with randomization and a single-blind sham controlled arm. 14 subjects underwent real TMS and 12 received sham. The real rTMS was employed with DANTEC TMS equipment at the R-DLPFC location. Subjects received 1 Hz TMS for 60 seconds on and 45 seconds off at 110% MT for approximately 30 minutes for a total of 1200 pulses per session. Subjects received 20 daily sessions in total. Both groups improved in fatigue and CGI but there was no improvement in pain and depression. Furthermore there was no significant difference between real and sham TMS in this sample. However, the sham system was suboptimal with simply a shift in the TMS coil to 45 degrees so that sound is heard but no cutaneous sensation was experienced. More importantly subjects received 400 fewer pulses per session for a total of 8000 fewer pulses than the Sampson group. Thus subjects may have been relatively “underdosed” in comparison, but they failed to replicate the TMS FM treatment effect with right-sided, prefrontal, slow-TMS treatment.

Passard et al⁹⁵, hypothesized that rTMS of the motor cortex might reduce chronic widespread pain in patients with fibromyalgia. They employed a randomized, double blind, sham-controlled parallel group study analyzing the analgesic effects of repeated daily sessions of unilateral rTMS in 30 patients with widespread pain, quality of life, mood, and anxiety problems due to fibromyalgia. Tender point pain threshold was a secondary outcome. Each treatment session employed a stimulation frequency of 10 Hz and 80% resting motor threshold intensity, resulting in a total of 2000 pulses per session. The primary outcome measure was self-reported average pain intensity over the prior 24 hours using an 11-point numerical scale. Average pain intensity was reported for 1 week as a baseline, during treatment (days 1-14) and until the first follow-up visit to make it possible to determine the onset of treatment effects, then was assessed at each follow-up visit on days 15, 30, and 60. Four patients (two per treatment group) withdrew from the trial between days 30 and 60. Pain intensity was similar in the two groups at baseline and rTMS had a significant effect on average pain intensity scores between baseline and day-15 in comparison with sham stimulation. This effect was not maintained on days 30 and 60. Average pain intensity was significantly lower in the active rTMS group than in the sham stimulation from day 5 to day 14. On day 15, McGill Pain Questionnaire total score and the sensory and affective subscores were significantly lower in the active rTMS group than in the sham-stimulation group. The difference in affective subscore persisted until day 30, whereas the sensory subscore did not. Subjective global pain relief over the last week was significantly greater in the active than in the sham-stimulation group up to day 30. Mean depression and anxiety scores were similar in the two treatment groups at baseline and were not significantly changed by active or sham stimulation. rTMS had no significant effect on the number of tender points. This study showed that rTMS of the primary motor cortex induced a long-lasting decrease in pain and improved quality of life in patients with fibromyalgia, without affecting mood or anxiety levels. One limitation of this study is the design of the sham system.

Table 1. Overview of current TMS fibromyalgia literature including the pilot study recently completed by the Investigators (Short et al)

Study	Sample Size	Cortical Target	Frequency	Intensity	Pulses Per Session	Sham System	Blind	Concurrent Meds
Sampson et al	4	Right Dorsolateral Prefrontal Cortex	1 Hz	110% rMT	1600	Did not control for Scalp Sensations	Treater was not blind	Permitted
Carretero et al	26	Right Dorsolateral Prefrontal Cortex	1 Hz	110% rMT	1200	Did not control for Scalp Sensations	Single-Blind	Permitted
Passard et al	30	Motor Cortex	10 Hz	80% rMT	2000	Did not control for Scalp Sensations	Double-Blind	Permitted
Short et al	20	Left Dorsolateral Prefrontal Cortex	10 Hz	120% rMT	4000	Controlled for Scalp Sensations	Single-Blind	Permitted

Per description, it makes similar sounds as active rTMS, however there is no form of superficial stimulation to the scalp, which can be problematic as otherwise the active and sham treatments are easily discerned.

There is evidence in the TMS-literature to suggest that slow (1 Hz) right prefrontal TMS has anti-depressant effects as does fast (10 Hz) left prefrontal TMS, however fast left prefrontal TMS appears to have larger effects that benefit more patients with depression than slow right. Following from these findings as well as several pilot studies conducted by our group showing analgesic benefits of fast left TMS in laboratory pain models⁹⁷, chronic neuropathic pain⁹⁸, and post-surgical pain⁹⁹⁻¹⁰¹, we recently completed a preliminary single-blind, sham-controlled trial of fast left dorsolateral prefrontal

rTMS among a cohort of 20 patients with fibromyalgia. Findings suggest significant, long-lasting benefits of real rTMS compared to sham on FIQ scores, average daily pain, and tender points (see Innovation section for a full description of this pilot study).

Noninvasive brain stimulation is in its infancy, particularly its application in the management of chronic pain disorders such as fibromyalgia. Techniques such as TMS and tDCS have shown some preliminary promise in the management of FMS, but more work is needed in this area. All the previous studies to date suffer some significant limitations that prohibit inferences regarding TMS efficacy for FMS pain. In all previous trials, patients were permitted to be on concomitant pain medications muddying the available TMS-efficacy inferences. The sham technologies employed in most previous trials did not permit for control over effects of scalp discomfort and other procedural pain associated with real TMS (not present during sham stimulation). Most trials to date have been single-blind, or have used methodologies that permit the interaction between patients and un-blinded investigators. The TMS cortical targets, frequencies, total pulses and intensities studied have varied considerably from study to study as have the methods for cortical localization. The typical outcome measures employed have been solely self-report and no objective measures of activity levels or sleep have been used, nor have experience sampling technologies been employed to capture unbiased daily pain ratings. Lastly, the sample-sizes employed in previous studies have been small and in some cases were convenience samples. *While the available preliminary data suggest the presence of a TMS effect on FMS pain, a more definitive, well-controlled investigation is needed to establish TMS as an efficacious, viable treatment option for patients with FMS.*

TDCS AND PERCEIVED PAIN CONTROL: Participants were 41 healthy individuals aged 20-57. A single 20-minute tDCS session was conducted using 2.0mA current during the same perceived controllability paradigm described above.⁶⁵ One electrode was applied to the left DLPFC and the other electrode was placed on the subject's right arm. Subjects received either anodal or cathodal PFC stimulation (randomized). Thermal stimulation delivered during perceived-control trials compared to no-perceived-control was rated less painful (by 2.75 points) across groups. Unpleasantness VAS ratings were significantly lower for participants randomized to the anode group (mean=56.49; SEM=4.26) compared to those randomized to the cathode tDCS group ((mean=69.39; SEM=3.83); $t(39)=2.25$, $p=0.03$) suggesting that anodal stimulation enhanced the analgesic benefits of perceived controllability and/or that cathodal stimulation of the left DLPFC disrupted those analgesic benefits. Participants randomized to the anode group rated their perceived control over the thermal pain stimuli at 4.7 out of 10 (SEM=0.49), whereas those randomized to the cathode tDCS group rated their perceived control lower at 3.24 (SEM=0.56; $t(39) = -1.95$, $p=.05$). These findings suggest that anodal tDCS of the DLPFC may enhance the analgesic effects of perceived-control and enhance the subjective sense of control.

COMBINED CBT and tDCS INTERVENTION EFFECTS ON PAIN PERCEPTION: To directly address the aims of the present proposal, in a recent preliminary pilot, the Investigators examined the effects of anodal versus cathodal tDCS over the left DLPFC in combination with a laboratory CBT intervention on thermal pain tolerance in 8 healthy volunteers. Participants underwent repeated heat tolerance testing using the Medoc Pathway system before, during and after the combined tDCS+CBT intervention. Participants were randomly assigned to receive anodal or cathodal tDCS delivered over the left DLPFC. For this preliminary pilot, participants all listened to a recording of a laboratory-version of a CBT intervention that focused on 3 distinct elements: 1) identification of catastrophizing language and replacement with more realistic and attenuated linguistic tags for thermal experiences. 2) identification and challenging of automatic negative self-effacing thoughts related to the tolerance task, and 3) a behavioral distraction strategy. Anodal tDCS applied to the left DLPFC during the CBT intervention was associated with a significant increase in thermal pain tolerance whereas cathodal stimulation appears to have blunted the analgesic benefit of the CBT intervention. Despite all subjects receiving the same CBT intervention, those that received simultaneous anodal stimulation of the left DLPFC found the CBT intervention significantly more helpful ($p<.05$) and found the strategies presented more useful in improving pain tolerance ($p<.05$) than those who received cathodal stimulation. These findings support the notion that engaging cognitive neural circuits that have been shown to play a role in the

down-regulation of pain experience and then exciting the circuits with tDCS might offer synergistic benefit.

D. RESEARCH DESIGN AND METHODS (including data analysis)

OVERVIEW: Pilot clinical trial-- Patients with FM will receive a brief course (6 sessions) of manualized CBT for pain (or education-only control) combined with anodal or sham tDCS over the left DLPFC

PARTICIPANTS: Participants will be 72 patients meeting the American College of Rheumatology (ACR) criteria from diagnosis of fibromyalgia for at least 1-year. Patients must not have any chronic pain conditions other than fibromyalgia, and must not be on chronic opioid therapy for pain. Patients with a history of seizures, who are or might be pregnant, or with metal/electronic implants or devices above the waist will be excluded to ensure tDCS safety. Patients with moderate to severe depression (HRDS>18) at the time of randomization will be excluded, however patients with no depression or only mild depression (HRDS<19) will be eligible provided that the onset of the first depressive episode was after the onset of fibromyalgia (as is commonly seen in patients with chronic pain) in order to exclude patients for whom chronic widespread pain might be a somatic manifestation of the depressive illness. To be eligible for enrollment, BAI scores must be <16 to limit the sample to patients with minimal to no clinical anxiety problems.

tDCS METHODS: tDCS will be delivered in 30-minute-sessions and will be conducted with the Phoresor-II Auto (Model PM850) using 2mA current. This constant current device ramps up to the desired amplitude to minimize discomfort for participants and ramps the amplitude back to 0mA at the end of the session. Electrodes will be standard small (4cm X 4cm) sponge electrodes soaked in a sterile solution of 0.9% sodium chloride insulated by a latex casing. The current density and total charge delivered by the above parameters is consistent with those used safely in the current research literature on tDCS. In all tDCS conditions, participants will undergo anodal stimulation of the left DLPFC (Brodmann Area 9; BA9) and cathodal stimulation of the right DLPFC (which is consistent with the majority of published prefrontal tDCS studies for pain to date) during each of the 6 CBT sessions. The electrodes will be fastened with Velcro strap(s). Specially designed software (by the Investigator) interfaces with an ONTRAK ADU218 Solid State Relay I/O interface connected to the tDCS device permitting normal and reverse current flow between the electrodes in a manner that is completely masked. The software reads the assigned condition directly from an encrypted subject-randomization-file and delivers anodal, cathodal or sham stimulation in a blinded fashion.

Clinical Pilot Trial: The proposed clinical pilot will investigate the effects of prefrontal tDCS combined with a standard manualized CBT intervention for chronic pain.⁷⁰ One session will be conducted each week for 6 weeks, and the double-blind tDCS delivery system will be used to ensure that tDCS randomization remains completely masked throughout the trial.

Cognitive-Behavioral Therapy Intervention: A 6-session version of the Otis standardized CBT manual for chronic pain will be used. Each session will last 60-minutes and standard CBT homework assignments will be employed as per the manual. A specially-trained pain-psychologist will implement the manualized CBT.

QUANTITATIVE SENSORY TESTING (QST): For female participants, all QST will be conducted during the luteal phase of the menstrual cycle. For patients in the clinical pilot, repeated QST sessions will be conducted at the same time of day. Participants will not be permitted to take any prn analgesic medication on the day of the QST session(s) prior to assessment. **THERMAL PAIN THRESHOLD ASSESSMENT:** Cutaneous heat stimuli will be delivered via a the ATS thermode of the Medoc Pathway System attached to the volar forearm of each subjects left arm. The Method of Limits will be

used. The thermode will heat at a rate of 0.5° C per second until the subject indicates that pain was perceived. The procedure will be repeated 5 times and mean values will be used. THERMAL WIND-UP PAIN ESTIMATION: The ATS thermode will be used to deliver 20 very brief noxious thermal stimuli to the left volar forearm of subjects at the rate of 1 stimulus (0.75 sec duration) every 1.5 seconds (at 49°C) thus facilitating C-fiber activation and receptive field expansion of the WDR neurons in the dorsal horn. Subjects will continuously indicate level of pain intensity using a dynamic computerized VAS. MECHANICAL PAIN THRESHOLD ASSESSMENT: The IITC Life Sciences Digital Anesthesiometer will be used to apply pressure to the dorsal surface of the distal phalange of the digit minimi of the left hand. Pressure will be increased at the rate of 10 grams per second. Participants will stop the stimulus when pressure reaches the pain threshold and the pressure will be recorded in grams. A FM trigger point evaluation will be conducted using an analog dolorimeter.

Dependent Measures:

THE BECK DEPRESSION INVENTORY (BDI) is a well-researched, brief self-report depression-screening instrument. This instrument will be used for screening purposes in the laboratory study and to characterize depression in the clinical cohort. The BDI scale assesses suicidal ideation, those patients exhibiting suicidal ideations will be referenced to a therapist in order to further manage their depressive symptoms.

THE BECK ANXIETY INVENTORY (BAI) is a well-researched, brief self-report anxiety-screening instrument. It assesses different aspects of anxiety experience (e.g., physiological, cognitive, behavioral).

THE BRIEF PAIN INVENTORY (BPI) is a self-report questionnaire designed to assess pain intensity and the impact of pain on general functioning, relationships and mood.

DAILY PAIN/MOOD DIARIES will be administered via paper and pencil to patients in the clinical pilot Diaries will assess daily (via VAS) average pain, pain at its worst, pain unpleasantness, mood, activity level, and will capture hours of sleep and sleep quality ratings.

THE MCGILL PAIN QUESTIONNAIRE (MPQ) is a self-report scale designed to capture the quality and intensity of pain experience. The ratings load onto 4 factors: 1) Sensory, 2) Affective, 3) Evaluative, and 4) Miscellaneous.

THE MOS SHORT-FORM12 HEALTH SURVERY (SF12) will be used to assess quality of life across the eight QOL domains captured with the measure during the trial.

THE FIBROMYALGIA IMPACT QUESTIONNAIRE will be used to assess pain symptoms and functioning specific to FM.

PROCEDURES:

Clinical Pilot Trial: Patients will be recruited by fliers or referred by providers in the Chronic Pain Clinic, Dept. of Rheumatology and the Behavioral Medicine Clinic at MUSC. Participants will be screened on the telephone, consented, oriented to the study, and instructed in the use of pain diaries. After a 2-week baseline phase, patients will undergo QST. They will then start the manualized CBT intervention in the Behavioral Medicine Clinic at MUSC with simultaneous tDCS (real or sham; randomized and masked). Participants will undergo 1 session per week for 6 weeks. After the last session, participants will undergo another QST session. Patients will continue to complete the pain diaries throughout the treatment as well as a 4-week follow-up phase. At 3 and 6 months, participants will return to the lab to re-complete the dependent measure battery.

DATA ANALYSIS PLAN AND POWER: Hierarchical Linear Modeling (HLM) will be used to examine changes in pain, sleep and activity over time while controlling for mood (time-series), and controlling for

baseline depression, anxiety and pain scores as a function of group (active vs sham tDCS). HLM will also be used to examine changes in quality of life and functional impairment due to pain. Previous research on the effects of CBT for pain and of tDCS for pain suggests that each is associated with a medium effect-size. To be conservative, assuming that there is no synergistic interaction-effect of combined tDCS and CBT, power is good to detect a group-level main effect ($1-\beta>.80$) with as few as 18 subjects per group. If the interaction-effect is large, as is expected, power is excellent to detect main and interaction effects ($1-\beta>.90$).

E. PROTECTION OF HUMAN SUBJECTS

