1. RISKS TO THE SUBJECTS

The sample will be 72 patients with chronic pain due to FM (BPI pain on average score $>4/10$) between the ages of 21 and 85, with a duration of illness of at least 1 yr and the diagnosis of FM. Interested participants will review and sign the informed consent document with one of the study investigators. Participants will be excluded if they have uncontrolled epilepsy, metal implants in the head or known brain tumors or lesions that intersect the area of stimulation, and severe latex allergies. If a participant indicates the possibility of pregnancy, a urine pregnancy test will be administered. Participants will be excluded from the study if they screen positive for pregnancy. Participants will also be screened for a history of closed head injury with loss of consciousness lasting more than 5 minutes, a history of seizures, a family history of seizures, metal implants above the waist, eczema or other sensitive skin conditions, and current medication usage. These screening measures will be used to assess the risk to benefit ratio for inclusion in the study on a case-by-case basis. If participants indicate on the BDI intent to harm themselves, they will be evaluated by a study psychologist. Pending results of the evaluation, participants will be admitted or hospitalized for appropriate care as necessary. There is no safety data to suggest increased risk for the older population, age 75-85, in this study. There is a possibility of increased skin irritation in this older population.

Targeted/Planned Enrollment Table

Total Planned Enrollment 72

TARGETED/PLANNED ENROLLMENT: Number of Subjects			
Ethnic Category	Sex/Gender		
	Females	Males	Total
Hispanic or Latino	2	1	3
Not Hispanic or Latino	42	27	69
Ethnic Category: Total of All Subjects*	72		
Racial Categories			
American Indian/Alaska Native	1	1	2
Asian	2	1	3
Native Hawaiian or Other Pacific Islander	1	1	2
Black or African American	19	9	28
White	22	15	37
Racial Categories: Total of All Subjects*	45	27	72

b. Sources of Materials

We will collect patient-reported depression, anxiety, sleep, activity, pain scores, and QST scores. All of the data will only contain a unique study identifier. The digital file containing identifying information will be kept on the PI's locked and secure computer. Only the PI and primary research assistant will have access to the identifying information.

c. Potential Risks

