tDCS has been found to be safe in humans with mild procedural side-effects such as tingling sensations under the sponge electrodes (experienced by 70% of tDCS patients), moderate fatigue (35%), and light itching sensations under the sponges (30%). After tDCS, the incidence of side-effects is lower but include headache (12%), nausea (3%) and insomnia (<1%) (Poreisz et al, 2007). If tDCS is delivered at 2mA for 20 minutes per day, every day for 4 or more days in a row, mild skin lesions have been reported. However, these lesions have all been reported to heal without scarring within 1 to 3 weeks following the end of tDCS treatment (Palm et al, 2008). All patients will be inpatient at MUSC and under the care of a licensed physician. Qualified nurses and physicians are available 24 hours a day to handle any and all potential complications if they occur.

The current-density of the proposed treatment is 0.125mA/cm² which is substantially less than the current density required to induce brain tissue damage (25mA/cm²). Further, the current (2mA) is over 400 times less than the average current used to induce seizures in electro-convulsive therapy (800mA). While this treatment is indeed investigational and the potential long-term effects are largely unknown, the parameters we plan to use appear to be extremely safe and are within the range used in the published tDCS-pain literature. The risks associated with the use of topical creams (benzocaine and vitamin-E/Aloe) are minimal but include skin irritation and contact dermatitis. If these occur, the investigators will immediately remove any cream from the subject's skin and apply a wet compress.

In a very recent study of tDCS effects on post-operative TKA pain, there were no adverse events associated with tDCS. The most common side effects reported by participants were mild tingling and itching under the electrodes. The benefits of this study appear to outweigh the risks as the slopes of the cumulative PCA usage curves were significantly different between the real and sham tDCS groups; those TKA in the real tDCS group used 44% less PCA dilaudid at 48-hours post-op than did the sham tDCS group. Despite significantly lower PCA dilaudid levels, VAS ratings of pain-on-average were also significantly lower in the real tDCS group ($t(37)=2.28$, $p=.029$).

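### Seizure history and metal implants above the waist are absolute exclusions in Section D but matters for case-by-case judgement in Section E

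*Combined protocol and SAP*

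**What the plan says.** Section D, Participants, sets an unconditional rule and gives tDCS safety as its purpose: "Patients with a history of seizures, who are or might be pregnant, or with metal/electronic implants or devices above the waist will be excluded".

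Section E.1, Risks to the Subjects, has its own list. Its absolute exclusions begin: "Participants will be excluded if they have uncontrolled epilepsy, metal implants in the head or known brain tumors or lesions". It then names conditions to be screened for, starting with closed head injury and continuing with "a history of seizures, a family history of seizures, metal implants above the waist, eczema or other sensitive skin conditions, and current medication usage". It explains their use: "These screening measures will be used to assess the risk to benefit ratio for inclusion in the study on a case-by-case basis". Section E.2a, Recruitment and Informed Consent, repeats this paragraph almost word for word.

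On process, Section D, Procedures, says: "Participants will be screened on the telephone, consented, oriented to the study". It does not say which list the telephone screener applies.

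On setting, the same section says of patients after baseline testing: "They will then start the manualized CBT intervention in the Behavioral Medicine Clinic at MUSC with simultaneous tDCS", at one session a week. Section E.1c, Potential Risks, says instead: "All patients will be inpatient at MUSC and under the care of a licensed physician".

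**The concern.** A condition cannot be both a flat bar to entry and a matter for judgement. If staff follow Section E, a patient whom Section D excludes for safety could be enrolled and stimulated. If they follow Section D, the same patient is turned away. Such an enrolment would be permitted by one part of the protocol and a deviation from another. The eligible population would also depend on which page the screener had read.

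This matters more than an ordinary drafting slip because the protocol itself describes tDCS as investigational and not FDA-approved for pain, and because it was the protocol's authors who tied the stricter rule to safety.

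**Working it through.** The plan gives no figure to reproduce here. The check is a comparison of the eligibility texts.

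| Condition | Section D, Participants | Sections E.1 and E.2a |
|---|---|---|
| Uncontrolled epilepsy | Excluded (falls under any seizure history) | Excluded |
| Controlled epilepsy or a past seizure | Excluded | Case by case |
| Metal implant in the head | Excluded (above the waist) | Excluded |
| Metal implant above the waist, outside the head | Excluded | Case by case |
| Electronic implant or device above the waist | Excluded | Not mentioned |
| Family history of seizures | Not mentioned | Case by case |

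**Where the rules conflict.** Rows 2 and 4 are direct contradictions: two criteria, in two versions of the rule. Row 5 is a gap. Section E names electronic devices neither among its exclusions nor among its items for judgement, so a screener working from it has no prompt to ask about them.

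**Whether the texts can be read together.** If Section D governed, Section E's narrower exclusions would be redundant and there would be nothing to weigh for seizure history or metal implants above the waist. Yet Section E lists both and says they are to be weighed for inclusion. Limiting the absolute exclusion to uncontrolled epilepsy also implies that controlled epilepsy may be considered.

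**Whether either list can be ignored.** Neither stands alone. The depression and anxiety limits, the opioid rule and the bar on other chronic pain conditions are in Section D only. The age range (21 to 85), the average pain threshold on the Brief Pain Inventory (above 4/10) and the latex-allergy exclusion are in Section E only. Staff need both lists to decide eligibility, so they will meet both rules.

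**Which rule prevails.** No text in either section, or elsewhere in the document, settles this.

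**Exposure of a patient admitted under the looser rule and assigned to active tDCS** (session length, current and number of sessions from Section D):

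- Time: 6 sessions × 30 min = 180 min = 10,800 s.
- Charge: 0.002 A × 10,800 s = 21.6 C in total, or 21.6 / 6 = 3.6 C per session.

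This is the ordinary protocol dose for every active participant. It shows what the patient would receive and is not an estimate of harm.

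**Setting.** Recruitment by flier or clinic referral, with weekly sessions in the Behavioral Medicine Clinic, describes outpatients. The inpatient sentence in Section E.1c does not fit the design. This is a separate and minor error.

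**The case against.** The strongest reply is that Section D, Participants, is the operative eligibility text and is unconditional, while Section E is supporting narrative. A site applying every criterion it finds would exclude the patient under Section D, so the looser route requires someone to overlook a flat exclusion. Even under Section E, uncontrolled epilepsy, metal in the head and lesions in the stimulated area stay absolute, and other cases get an explicit risk-benefit assessment. This does not remove the conflict. Section E.1 carries binding criteria found nowhere else, and Section E.2a is the recruitment section, so neither can be set aside as background. Section E also expressly contemplates inclusion after assessment.

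Several narrower points stand:

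- The exposure figures say nothing about added risk. Section E.1c gives a current density of 0.125 mA/cm² against a stated tissue-damage level of 25 mA/cm², and a current more than 400 times below that used in electroconvulsive therapy. Those comparisons are not specific to people with seizure history or implants, so they do not justify relaxing Section D either.
- The documents do not show that individual review of an implant outside the head is unsafe. Consistency could be restored in either direction; the stricter rule is preferred because the protocol links it to safety.
- No telephone script is in the documents. The point is that the protocol leaves the choice of list open, not that the wrong list is known to be in use.
- Pregnancy wording also differs: Section D excludes possible pregnancy, while Section E tests and excludes positives. These can be reconciled if the test resolves the possibility, so this is not counted as a third conflict.
- Clinical cover is not absent. Section H, Facilities Available, describes a clinic staffed by nurses, pharmacists, psychiatrists and psychologists, and Section E.2b repeats the statement of 24-hour cover.

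**Conclusion.** The concern holds. Two tDCS safety criteria, seizure history and metal implants above the waist, are absolute in Section D and discretionary in Sections E.1 and E.2a, and electronic devices are missing from Section E altogether. Following the protocol as written could lead to stimulating a patient whom it elsewhere bars for safety, so it must be corrected.

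The conclusion rests on the text alone. It assumes only that no governing statement exists outside the documents available. The share of candidates affected and any excess risk to them cannot be computed, and no injury is claimed. Sample size, power and the planned analysis are untouched.

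**What to change.** Apply the Section D rule throughout:

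- In Sections E.1 and E.2a, and in the telephone screen, list any history of seizures and any metal or electronic implant or device above the waist as absolute exclusions.
- Remove seizure history and metal implants above the waist from the case-by-case list. Family history of seizures, closed head injury, skin conditions and medication use can remain there.
- Ideally, keep one complete eligibility list and have the other sections refer to it. In the same edit, state that possible pregnancy is resolved by the urine test.
- In Section E.1c, replace the inpatient sentence with the weekly outpatient clinic setting and the cover actually available there. Check the repeated 24-hour statement in Section E.2b against it.

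The cost is a text amendment and a revised telephone screen, with no new procedures and no change to the analysis. Some candidates who might have been admitted by judgement would be lost. The documents do not allow that number to be estimated, but Section D already excludes every one of them.
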